6.3 Secondary Efficacy Analysis

The secondary efficacy analysis will be performed for the following endpoints:

Progression-Free Survival (PFS) will be defined as the number of days from the date of first dose of study drug to the date of earliest disease progression or death. All events of disease progression will be included regardless whether the event occurred while the subject was taking the study drug or had previously discontinued the study drug. If the subject has not experienced disease progression or death, the subject's data will be censored at the date of last disease assessment. Data for subjects who receive non-protocol specified T-PLL therapy (i.e., excluding stem cell transplantation for eligible CR subjects) prior to disease progression will be censored at the last disease assessment prior to receiving non-protocol therapy. Data for subjects without any disease assessments performed after the baseline visit will be censored at the time of dosing plus 1 day. PFS

will be analyzed by Kaplan-Meier methodology. Median PFS will be calculated and 95% confidence interval for median PFS will be presented.

Duration of Response (DoR) will be defined as the number of days from the date of first response (CR, CRi, or PR) to the earliest date that progressive disease (PD) or death. For subjects who have a PR before CR, or CRi, in subsequent visits, the DoR is computed from the earliest PR. If the subject has not experienced disease progression or death, the subject's data will be censored at the date of last disease assessment. For subjects who do not have subsequent disease assessment after their first response, the subject data will be censored at the first response. For subjects who never experience response, the subject's data will not be included in the analysis. DoR will be analyzed by Kaplan-Meier methodology. Median DoR will be calculated and the corresponding 95% confidence interval will be presented.

Time- to- Progression (TTP) will be defined as the number of days from the date of first dose of study drug to the date of earliest disease progression. All events of disease progression will be included regardless whether the event occurred while the subject was taking the study drug or had previously discontinued the study drug. If the subject has not experienced disease progression, the subject's data will be censored at the date of last disease assessment. Data for subjects who receive non-protocol specified T-PLL therapy (i.e., excluding stem cell transplantation for eligible CR subjects) prior to disease progression will be censored at the last disease assessment prior to receiving non-protocol therapy. Data for subjects without any disease assessments performed after the baseline visit will be censored at the time of dosing plus 1 day. TTP will be analyzed by Kaplan-Meier methodology. Median TTP will be calculated and 95% confidence interval for median TTP will be presented.

Event-free survival (EFS) will be defined as the number of days from the date of first dose of study drug to the date of earliest disease progression, death, or start of a new anti-T-PLL therapy. If the specified event (disease progression, death, start of a new anti-T-PLL treatment) does not occur, patients will be censored at the date of last disease assessment or date of stem cell transplantation. Data for subjects without any disease assessments

performed after the baseline visit will be censored at the date of first dose plus 1 day. EFS will be analyzed by Kaplan-Meier methodology. EFS will be calculated and 95% confidence interval for median EFS will be presented.

Overall Survival (OS) will be defined as the number of days from the date of first dose of study drug to the date of death due to any cause. All events of death will be included, regardless of whether the event occurred while the subject was still taking any study drug, or after the subject discontinued study drug. For subjects who did not die, their data will be censored at the date of last study visit or the last known date to be alive, whichever is later. OS will be analyzed by Kaplan-Meier methodology. Median OS will be calculated and 95% confidence interval for median OS will be presented. Data from subjects that are alive at the time of analysis will be censored at the date of last study visit or the last known date the subject was alive, whichever is later.

6.4 Sensitivity Analysis:

For all the time-to-event endpoints (PFS, TTP, DoR, EFS and OS) a sensitivity analysis may be performed for the CR subjects who have undergone stem-cell transplantation by censoring them at their last disease assessment prior to the transplant.

Transplant-naïve subjects to proceed to further autologous/allogeneic stem cell transplantation will be measured by the - proportion of eligible subjects reaching autologous or allogeneic transplantation. The eligible subjects are defined as the transplant-naïve subjects who have achieved CR and then proceed to further autologous/allogeneic stem cell transplantation.

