3.3 Secondary Endpoints

Key secondary endpoints are as follows:

- PFS, defined as the time from the date of first dose of any study drug to the date of earliest disease progression or death
- duration of response, defined for subjects who achieve a best overall response of CR, CRi, or PR, as the time from the date of first response (CR, CRi, or PR) to the earliest date of disease progression or death
- time-to-progression, defined as the time from the date of first dose of any study drug to the date of earliest disease progression

- event-free survival, defined as the time from the date of first dose of any study drug to the date of earliest disease progression, death, or start of a new anti-T-PLL therapy
- disease control rate, defined as the proportion of subjects achieving CR, CRi, PR, or stable disease as best overall response
- overall survival, defined as the time from the date of first dose of any study drug to death from any cause
- number of eligible subjects reaching autologous or allogeneic transplantation; eligible subjects are the transplant-naïve subjects who have achieved CR

All secondary endpoints will be assessed per investigator assessment in R/R T-PLL subjects based on the T-PLL consensus criteria 2019.¹¹

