3.14 Disease Assessment

All measurable disease must be documented at screening (baseline) before the first dose of study drug for all subjects based on the analysis of clinical laboratory tests (hematology), physical examination, and contrast-enhanced CT scan of involved neck, chest, abdomen, and pelvis (or MRI, if CT scan is medically contraindicated).

For all subjects, clinical response (laboratory and physical examination assessments) will be assessed by the investigator during Weeks 4, 8, 12, 16, 24, 36 and every 12 weeks thereafter, and at the final visit. Note: disease assessments may be performed approximately 7 days before the scheduled visit. The clinical response will be assessed by laboratory tests and physical examination (or ultrasound) using the T-PLL consensus criteria¹ (as outlined in [Table 2](#)).

If clinical response is suggestive of a CR/CRi, a CT scan with contrast (or MRI) should be done for a confirmatory assessment as outlined in [Section 3.13](#).

If a CT scan indicates a CR/CRi, a bone marrow aspirate and biopsy will be required as soon as possible to confirm the clinical response. For subjects who opt-in for correlative biomarker analyses, a portion of the bone marrow aspirate should be split for the optional biomarker collections listed in [Section 3.17](#).

To meet the CR criteria, the CT scan and bone marrow are both required to be negative. Some subjects fulfill all the criteria for a CR but have a persistent anemia, thrombocytopenia, or neutropenia apparently unrelated to T-PLL, but related to drug toxicity. These subjects will be assessed with a response of CRi.

Disease assessment will continue to be performed after the last dose of study drug until disease progression for any subject who has not experienced PD at the time of permanent discontinuation of venetoclax and ibrutinib.

Table 2. Clinical Response Criteria (Based on Physical Examination/Ultrasound and Laboratory Tests)

Group	Parameter	Complete Remission (all met)	Partial Remission (≥ 2 in Group A and ≥ 1 in B met)	Stable Disease (all met)	Progressive Disease (≥ 1 in Group A or B met)
A	Lymph nodes by physical examination/ultrasound	All long-axis diameters to < 1.0 cm	Decrease $\geq 30\%$ in SLD	Change of -29% to $+20\%$ in SLD	Increase in $> 20\%$ in SLD from Nadir ^a

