4.7 Missing Data Imputation

The missing data imputation will not be performed for this study. For time-to-event endpoints, censoring will be defined for missing data.

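### The rule for subjects with no post-baseline assessment is not limited to event-free subjects, so early deaths can drop out of PFS and EFS; the DoR rule has the same gap

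*SAP*

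**What the plan says.** Protocol section 3.3 defines the endpoint as "PFS, defined as the time from the date of first dose of any study drug to the date of earliest disease progression or death". SAP section 6.3 uses the same events. EFS adds the start of new anti-T-PLL therapy, and DoR runs from first response to progression or death.

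In each of these SAP paragraphs the main censoring sentence applies only if no event of that endpoint has occurred. Each paragraph also has a further sentence without that condition:

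- **PFS:** "Data for subjects without any disease assessments performed after the baseline visit will be censored at the time of dosing plus 1 day".
- **EFS:** subjects with no disease assessment "performed after the baseline visit will be censored at the date of first dose plus 1 day".
- **DoR:** "For subjects who do not have subsequent disease assessment after their first response, the subject data will be censored at the first response".

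The PFS paragraph has an inclusion sentence for progression: "All events of disease progression will be included regardless whether the event occurred while the subject was taking the study drug". It has none for death. The OS paragraph does: "All events of death will be included, regardless of whether the event occurred while the subject was still taking any study drug". On missing data in general, SAP section 4.7 says only: "For time-to-event endpoints, censoring will be defined for missing data".

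**The concern.** A treated subject who dies before any post-baseline assessment fits two statements at once. By definition the subject has a PFS and EFS event on the date of death. By the sentence for subjects without an assessment, the subject is censored one day after first dose. The SAP does not say which prevails. The same clash arises in EFS when new therapy starts with no assessment on record, and in DoR when a responder dies before the next assessment.

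Two programmers could therefore produce different PFS, EFS and DoR curves from the same data. The literal choice always favours the treatment, because it removes the worst outcomes from the event count. In a single-arm trial no control group shares that bias.

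**Working it through.** The documents give no figure for this point, so there is nothing to reproduce. The check has a textual part and a sizing part.

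**1. Rules side by side (SAP 6.3)**

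| Endpoint | Events | Main censoring rule | Rule when the assessment is lacking |
|---|---|---|---|
| PFS | progression, death | only if neither occurred | dosing + 1 day, no condition |
| EFS | progression, death, new therapy | only if none occurred | first dose + 1 day, no condition |
| DoR | progression, death | only if neither occurred | first response, no condition |
| TTP | progression | only if it did not occur | dosing + 1 day, no condition |

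The rule does no harm in TTP, where death is not an event and progression has to be found at an assessment. The PFS sentence is word for word the TTP sentence, carried into an endpoint where death does count.

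The PFS sentence just before it, on non-protocol T-PLL therapy, also lacks an event-free condition, and it does censor subjects ahead of later events. So the condition in the main rule cannot be assumed to carry forward.

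**2. Who is reached**

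The Full Analysis Set needs only one dose (SAP 5.1), so these subjects stay in the analysis. Operations Manual section 3.14 schedules clinical response assessments at Weeks 4, 8, 12, 16, 24 and 36, then every 12 weeks, and at the final visit. It adds that "disease assessments may be performed approximately 7 days before the scheduled visit".

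- PFS and EFS: only subjects with neither a Week 4 nor a final-visit assessment. EFS events from new therapy are lost only if the final-visit assessment is also missed.
- DoR: a responder who dies before any later assessment. After Week 24 scheduled assessments are 12 weeks apart.

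**3. Effect on the PFS and EFS curves**

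Let N be the number of treated R/R subjects (31, 34 or 37 in SAP Table 1) and d the number who die before any post-baseline assessment (assumed). Suppose nobody else is censored before the last of these deaths, and m subjects remain event-free just after it. Then event-first survival is m/N and literal survival is m/(N−d). All later Kaplan-Meier factors are the same, so

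literal / event-first = N/(N−d).

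| d | N = 31 | N = 34 | N = 37 |
|---|---|---|---|
| 1 | 31/30 = 1.033 | 34/33 = 1.030 | 37/36 = 1.028 |
| 3 | 31/28 = 1.107 | 34/31 = 1.097 | 37/34 = 1.088 |
| 5 | 31/26 = 1.192 | 34/29 = 1.172 | 37/32 = 1.156 |

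With three such deaths of 37 and no other early event, Week 4 PFS is 34/37 = 91.9% event-first and 100% literally.

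**4. Effect on the median**

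This was simulated with 2,000 trials per setting. Assumptions: early deaths uniform on days 2.5 to 27; the other subjects' events at day 28 plus an exponential time with median 4, 6 or 12 months; censoring uniform on days 180 to 900. Medians in months, event-first / literal:

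| Setting | 4 months | 6 months | 12 months |
|---|---|---|---|
| 3 of 37 | 4.4 / 4.8 | 6.2 / 6.7 | 11.3 / 12.7 |
| 5 of 31 | 3.9 / 4.7 | 5.4 / 6.6 | 10.0 / 12.7 |

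One death of 37 leaves the median identical in 100%, 96% and 67% of trials. An independent rerun agreed within simulation error, and ending the early-death window at day 21 gave matching results.

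**5. Effect on DoR**

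Take 12 responders, the smallest number that is significant at n = 37 (Protocol Table 6 footnote). One death soon after response with no later assessment multiplies the later curve by 12/11 = 1.09. Two such deaths multiply it by 12/10 = 1.20.

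**The case against.** The best defence is that the sentence only supplies a censoring date for event-free subjects who have no last assessment to be censored at. That is a natural reading. SAP 4.7 ties censoring to missing data, and a known date of death is not missing. The inclusion sentences for PFS and OS concern events on or off treatment, so silence on death there is weak evidence, and reuse of the TTP wording suggests a template more than an intention. All of this makes the event-first reading plausible. None of it sets precedence.

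SAP section 3.0 leaves programming conventions to a separate Statistical Programming Plan, which may settle the point and is not among the documents. Whether a death counts as an event, however, is part of the endpoint's definition and belongs in the SAP.

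It is also true that a literal analysis could put PFS above OS early on, an impossible ordering that would show in the output. That would expose the problem only after results were seen.

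The objections on size stand in part. The exposure window is short, five deaths of 31 is a high assumption, the endpoints are secondary and descriptive, and SAP 4.6 calls the study hypothesis-generating. These limit the severity but do not remove the contradiction.

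**Conclusion.** The concern holds. Followed as written, the PFS, EFS and DoR rules can censor deaths that the definitions count as events, and the result always favours the treatment. An event-first reading is available but not secured.

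The size depends wholly on the assumed number of early deaths: negligible to small for one, and for three to five of 31 to 37 subjects a later PFS or EFS curve about 9% to 19% too high in relative terms. The shift in the median depends further on the assumed event times.

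The primary analysis is untouched, because such subjects are nonresponders for ORR, and OS counts every death. This should be fixed, but it does not threaten the trial's main conclusion.

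**What to change.** Amend SAP section 6.3 as follows:

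1. **PFS:** apply the dose-plus-1-day rule only to subjects with neither progression nor death. Count a death before any post-baseline assessment as an event on its date, unless non-protocol T-PLL therapy began earlier. In that case the SAP's existing non-protocol-therapy rule takes precedence, with first dose plus 1 day as the censoring date if there was no earlier assessment. Saying so prevents a new clash with that rule.
2. **EFS:** apply the rule only to subjects with no progression, death or new anti-T-PLL therapy.
3. **DoR:** censor at first response only those responders with no later assessment who have not died. Count a death as an event on its date.
4. **TTP:** no change.

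The cost is three SAP sentences and no new data. PFS, EFS and DoR may look slightly less favourable than under the literal rule.

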Ibrutinib 420 mg will be dosed orally (PO), once daily (QD) starting on Day –1. Venetoclax will be initiated on Week 1, Day 1 with an initial 5-day dose ramp-up for venetoclax ([Figure 1](#)). Venetoclax 400 mg (target dose) will be dosed PO, QD; an option to increase the dose of venetoclax to 600 mg QD will be available at Week 8 or thereafter if there is evidence of incomplete response and/or if the dose of ibrutinib has been decreased to 280 mg/day or 140 mg/day due to toxicity management. The dose of venetoclax should not be increased to 600 mg/day in subjects with significant venetoclax toxicity. The maximum dose allowed for venetoclax is 600 mg/day.

Treatment duration of combination treatment will be as follows:

- eligible subjects will proceed to stem cell transplantation after reaching CR (combination therapy will be discontinued but subjects will be followed for disease progression)
- up to 2 years, will be given to subjects who are ineligible for stem cell transplantation unless treatment is intolerable or the subject develops progressive disease

[figure not shown]
For subjects who continue to derive clinical benefit after 2 years of treatment, AbbVie will work with the investigator to consider the potential continuation of therapy, as per local regulations.

See Section 5 for information regarding eligibility criteria.

The dosing schematic is shown in Figure 1. To mitigate the risk of tumor lysis syndrome (TLS) (see Section 6.2) with venetoclax, a 5-step dose ramp-up with hospitalization for close monitoring and prophylaxis has been developed. Due to the aggressive nature of T-PLL, the venetoclax ramp-up will be administered in a daily manner, starting with 20 mg on Week 1, Day 1 and reaching the target dose of 400 mg on Week 1, Day 5. Refer to Section 6.2 for details for TLS management.

Further information regarding study procedures is located in the Operations Manual Section 3.

Figure 1. Dosing Schematic

CR = complete remission; D = day; W = week

Note: Venetoclax 5-step dose ramp-up in 5 days to target dose of 400 mg daily with an option to increase the dose to 600 mg QD at Week 8 or thereafter if there is evidence of incomplete response and/or if the dose of ibrutinib has been decreased to 280 mg/day or 140 mg/day due to toxicity management.

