3.11 Post-Treatment Follow-Up and Survival Visits

Subjects who discontinue study drug but have not experienced progressive disease (PD) will return for post-treatment follow-up visits. The post-treatment follow-up visits will follow the same schedule as the visit schedule (i.e., Week 4, Week 8, Week 12, Week 16, Week 24, Week 36, and every 12 weeks thereafter). Subjects will return for post-treatment follow-up visits until study completion starting from study drug discontinuation until documented PD or other post-treatment therapies (including stem cell transplantation) are received. Follow-up hematology and disease response assessment data will be collected.

Survival information (i.e., the date and cause of death) will be collected via telephone calls at 6-month intervals or as needed to allow for more frequent survival analyses.

All subjects will be followed for survival information (i.e., date and cause of death, all poststudy anticancer treatment including stem cell transplantation, reasons for poststudy anticancer treatment, regimens, dates of initiation and completion, etc.) unless the subject requests to be withdrawn from the

study survival follow-up; this request must be documented in the subject's medical record and signed by the investigator. If the subject withdraws from study follow-up, the study staff may use a public information source (such as county records) to obtain information about survival status only, as appropriate per local regulations.

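### The optional transplant sensitivity analysis (SAP 6.4) censors overall survival at the last disease assessment, so it discards time in which transplanted subjects are known to be alive

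*SAP*

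**What the plan says.** SAP 6.4 opens: "For all the time-to-event endpoints (PFS, TTP, DoR, EFS and OS) a sensitivity analysis may be performed". It applies to CR subjects who have had a stem cell transplant, and it gives all five endpoints one rule: "censoring them at their last disease assessment prior to the transplant". There is no separate date for OS, and no aim is stated.

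The main OS analysis in SAP 6.3 works differently. On deaths it says: "All events of death will be included, regardless of whether the event occurred while the subject was still taking any study drug". For subjects who have not died, "their data will be censored at the date of last study visit or the last known date to be alive, whichever is later". Nothing in it censors OS at transplant.

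Transplant belongs to the treatment plan. Protocol 4.1 says that "eligible subjects will proceed to stem cell transplantation after reaching CR". Operations Manual 3.14 schedules response assessment "during Weeks 4, 8, 12, 16, 24, 36 and every 12 weeks thereafter, and at the final visit". Operations Manual 3.11 says "All subjects will be followed for survival information", and the items it lists include later stem cell transplantation and treatment dates.

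**The concern.** After the last assessment a subject's progression status is unknown, so stopping the clock there is defensible for progression-free survival (PFS), time to progression (TTP), duration of response (DoR) and event-free survival (EFS). Vital status is different: a subject who is transplanted was alive on that day.

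Under SAP 6.4 the OS censoring date depends on what happens later. Take two CR subjects with the same last assessment, both awaiting transplant. One dies before it and stays in the analysis as a death. The other survives to transplant and is removed from that same interval retrospectively. Deaths stay in and survivors leave.

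At stake is how the sensitivity analysis is read. A natural use, which the SAP does not state, is to show OS without the contribution of transplant. Under the present rule, any gap from the main curve would mix the removal of post-transplant experience with an artefact of the censoring date.

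**Working it through.** The plan gives no OS figure to reproduce, so the check compares three censoring rules for transplanted subjects:

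- **A**: the main SAP 6.3 rule, with no censoring at transplant
- **B**: censor at the transplant date
- **C**: censor at the last disease assessment before transplant (SAP 6.4)

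**Step 1: direction of C against B.** Each Kaplan-Meier factor is 1 − d/n, with d deaths among n at risk. At a death time t, let m be the number of transplanted subjects whose last assessment came before t and whose transplant came at or after t. They are alive at t, so d is the same under both rules, while n(C) = n(B) − m. Hence 1 − d/n(C) ≤ 1 − d/n(B) at every death time, and curve C lies on or below curve B throughout.

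**Step 2: a small example.** Ten subjects, two of them transplanted after month 6. Two deaths occur before the last assessment of the transplanted pair, and three between that assessment and month 6.

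- B: (8/10) × (5/8) = 0.50 at 6 months
- C: after the two deaths, 8 − 2 = 6 remain at risk, so (8/10) × (3/6) = 0.40

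**Step 3: likely size of C against B.** All inputs here are assumptions: 34 subjects; exponential OS with median 9 months; 10%, 20% or 30% selected for transplant at Weeks 12 to 40 regardless of prognosis; selected subjects who die first stay in as deaths. True 12-month OS is 0.5^(12/9) = 39.7%. Each cell rests on 2,000 to 4,000 simulated trials.

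| Gap from last assessment to transplant | Mean change in 12-month OS, points (10% / 20% / 30%) | 2.5th percentile, points |
|---|---|---|
| Scheduled on-treatment visits only (mean gap about 4 weeks) | −0.3 / −0.7 / −1.1 | −1.2 / −2.1 / −3.0 |
| Assumed uniform on 0 to 4 weeks | −0.15 / −0.31 / −0.49 | −0.6 / −1.0 / −1.4 |

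Rule B recovers the true value (39.7% to 39.8%). No simulated trial moved upward under C.

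A harsher set of 36 assumed scenarios fixed the share transplanted (10% to 35%, at months 4 to 8) and gave every transplanted subject the same gap of 1 or 2.76 months. C was below B in all of them, by 0.5 to 5.3 points at 12 months. The largest values need 35% transplanted, each with the full 12-week gap.

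**Step 4: direction of C against the main analysis A.** Two of those scenarios, both with a 1-month gap, show 12-month OS as follows:

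| Assumed scenario | A | B | C | B − A | C − B | C − A |
|---|---|---|---|---|---|---|
| Median OS without transplant 6 months, 20% transplanted, post-transplant median 36 months | 0.375 | 0.298 | 0.287 | −0.077 | −0.011 | −0.088 |
| Median OS without transplant 10 months, 35% transplanted, post-transplant median 6 months | 0.455 | 0.519 | 0.502 | +0.064 | −0.017 | +0.047 |

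The artefact (C − B) is negative in both. The total departure from the main curve (C − A) changes sign with post-transplant survival, for which the documents give no rate.

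**The case against.** **A reader might infer that the trial's OS estimate is biased downward.** The documents do not support that. The main OS analysis counts every death, censors at the last date known alive and is untouched. The downward direction holds only against censoring at transplant, a rule the SAP does not contain. Against the main curve, SAP 6.4 can give higher OS, as Step 4 shows.

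**A reader might also infer a loss of up to 12 weeks per transplanted subject, from the visit spacing after Week 24.** That counts only scheduled on-treatment visits. Combination therapy stops for transplant (Protocol 4.1). The final visit falls at the end of study treatment and includes a response assessment, and post-treatment follow-up visits then run until progression or further therapy (Operations Manual 2.1, 2.2, 3.11). If their schedule restarts at discontinuation, which the text leaves unclear, the nominal gap is at most about 4 weeks. That roughly halves the effect.

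**The effect is small beside sampling error.** With 34 subjects and 12-month OS near 40%, the 95% half-width is about 1.96 × √(0.397 × 0.603 / 34) = 0.164, or 16 points. The analysis is optional, OS is secondary, SAP 4.6 calls the study hypothesis generating, and further conventions are left to a programming plan not available here.

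**Censoring at transplant is itself open to doubt.** Subjects who reach CR and are fit for transplant are a selected group, so their censoring is unlikely to be independent of prognosis. Changing the date does not cure that.

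All four points stand as limits on importance. None makes a disease-assessment date right for OS, and SAP 6.4 names OS explicitly.

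**Conclusion.** The point holds in limited form. For OS, SAP 6.4 sets a censoring date that conflicts with the principle in SAP 6.3 and discards known-alive time only from subjects who survive to transplant. That the curve is lower than or equal to the one censored at transplant follows from the Kaplan-Meier formula and needs no assumption about rates.

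The size does rest on assumptions. Under those of Step 3, 12-month OS falls by about 0.15 to 1.1 points on average, depending on the share selected for transplant and on whether final-visit and post-treatment assessments shorten the gap. Larger shifts need many transplants with long gaps. No claim about direction against the main OS analysis is justified. The primary response rate, the futility rule and the main OS analysis do not change. This is a minor correction, worth making because it is cheap and because the analysis, if run, should not carry an avoidable artefact.

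**What to change.** In SAP 6.4:

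- For OS only, censor transplanted CR subjects at the date of transplant.
- State that this assumes censoring at transplant is independent of prognosis, that this is doubtful for selected CR subjects, and that the result should be read with that in mind.
- Keep the last disease assessment before transplant for PFS, TTP, DoR and EFS.

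The cost is one clause and one sentence. No new data are needed: survival follow-up already collects stem cell transplantation and treatment dates (Operations Manual 3.11), and SAP 6.3 already uses the transplant date as a censoring date for EFS.
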